1.3 Correlative Objectives

- To conduct an exploratory biomarker correlative study of clinical outcome utilizing archival tumor tissue and serum collected at baseline and serially during therapy
- To examine biomarkers in tissue post-treatment at the time of re-biopsy, if performed
- To examine serum biomarkers of the peripheral immune response after aromatase inhibition

2 Background and Rationale

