2.5 Rationale

While modest improvements have been made in survival and quality of life in patients with advanced non-small cell lung cancer (NSCLC) there is a need to explore new agents and combinations with novel mechanisms of action in an effort to improve clinical outcomes in this patient population. With the introduction of immune checkpoint blockade and the durability of response, the vast majority of patients with NSCLC are receiving immune checkpoint blockade at some point in their therapy. However, response rate is relatively low spawning interest in developing novel combination therapies that can improve upon the response or generate responses in patients who are failing therapy. It is generally accepted that the aromatase inhibitor (AI) exemestane is less toxic than chemotherapy, yet potentially it can provide equal or greater benefit. In hormone receptor positive breast cancer, anti-estrogen therapy is a first-line treatment for metastatic disease,

and is given as adjuvant therapy for 5 years in earlier stage disease. Exemestane has been used in tens of thousands of women and its efficacy and side effect profile has been well established. Furthermore, preclinical and clinical data suggest that there might be a role of estrogen receptor signaling in maintaining immune suppression in the tumor microenvironment. Therefore, we propose a 2-stage phase II trial of exemestane in previously treated postmenopausal women with metastatic NSCLC who are progressing on anti-PD1 or anti-PDL1 therapy to determine if aromatase inhibition will result in treatment responses in this patient population and to determine whether ER-related biomarkers can identify patients likely to receive clinical benefit.

The estrogen pathway inhibition is a promising novel target in NSCLC. Preclinical evidence support targeting the synthesis of estrogen in NSCLC as a strategy that may result in enhanced antitumor activity.

3 Study Design

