This is a phase II study of daily oral exemestane for the treatment of advanced non-small cell lung cancer in post-menopausal women who are progressing on an FDA approved immune checkpoint blockade therapy. The study will be conducted using Simon's two-stage design.³⁰ Stage 1 will enroll 10 patients. If at least 2 objective responses are observed at the first disease re-evaluation at 6 weeks after beginning oral exemestane, Stage 2 will be activated. In Stage 2, an additional 19 patients will be enrolled for a total of 29 patients. If 4 or more objective responses are observed in the 29 patients, exemestane will be deemed worthy of further investigation in this patient population.

4 Patient Selection

Study entry is open to post-menopausal women regardless of race or ethnic background. While there will be every effort to seek out and include minority women, the patient population is expected to be similar to that of advanced non-small cell cancer lung studies at the University Of Minnesota. Men are not eligible for this study as exemestane works by suppressing estrogen production. Women of child-bearing potential are not eligible as exemestane is FDA pregnancy category X – known harm to the unborn.

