13.1 Study Design, Objectives and Endpoints

The goal of this phase II study is to estimate the probability of response after treatment of exemestane in post-menopausal women with advanced non-small cell lung cancer progressing while on immune checkpoint blockade. The primary endpoint of treatment response will be assessed at 6 weeks after the start of treatment using RECIST criteria. Secondary endpoints include the proportion of toxicities through 30 days after the last dose or start of new treatment as described in Section 10.2.2, disease-control as measured by response duration, progression-free and overall survival through 12 months from study enrollment and quality of life scores as measured by PROMIS-29 at baseline, every 3 weeks during treatment and at the end of treatment visit. The primary endpoint of response will be evaluated using a two-stage design.

Stage 1 will enroll 10 patients. If 2 or more patients have an objective response after completion of stage 1, an additional 19 patients will be enrolled in stage 2 for a total of 29 patients. If the total number of patients responding is 4 or greater, the treatment will be considered worthy of further investigation.

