13.2 Sample Size

Sample size is based on testing our primary endpoint using Simon's optimal two stage design with a type I error of 5% and power of 80%.³⁰ Our null hypothesis is that the response is $\leq 5\%$ (as all will be progressing on anti-PD1 therapy) and our alternative hypothesis is that response is $\geq 20\%$. If the treatment is truly not effective, there is a 5% chance of concluding that the drug is effective while if the treatment is truly effective, there is a 20% chance of concluding that it is not effective. Up to 10 patients will be enrolled per year.

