13.3 Statistical Analysis

The primary endpoint of response will be estimated with a simple proportion and a 95% confidence interval. The secondary endpoints of survival and progression-free survival will be estimated with Kaplan-Meier curves. Disease control will be assessed with descriptive statistics and plots such as medians, ranges, interquartile ranges and box-plots. Toxicities will be assessed with descriptive statistics and plots such as simple proportions and bar graphs. Quality of life scores, as measured by PROMIS, will be evaluated descriptively at baseline, every 3 weeks during and at the final visit using medians, ranges, interquartile ranges and boxplots to look for trends in various areas measured by PROMIS. Analysis of correlative objectives will involve assessment of associations of baseline measurements of five biomarkers from tumor tissue and clinical outcome. Biomarkers will be evaluated by evaluation of quartiles with subsequent dichotomization and then comparison by response using a Chi-square test or Fisher's exact test depending on sample size. Evaluation of biomarkers is primarily descriptive and will be used in the planning of future studies both for selection criteria and validation. Six biomarkers from blood will similarly be assessed; however, these measurements will be assessed at individual post-treatment time-points as well. If warranted, repeated measures analyses may be used to look at measurements over time. There is currently no plan to demonstrate that the biomarkers could be used as surrogate endpoints but rather if associations exist for future evaluation.

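### Section 13.3 relates the biomarkers to outcome only through 6-week response, so a Stage 1 futility stop leaves that comparison empty or uninformative; outcomes already being collected could be added

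*Combined protocol and SAP*

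**What the plan says.** The correlative objective in Section 1.3 is "To conduct an exploratory biomarker correlative study of clinical outcome utilizing archival tumor tissue and serum collected at baseline and serially during therapy". Section 2.5 adds a wider aim: "to determine whether ER-related biomarkers can identify patients likely to receive clinical benefit".

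Section 13.3 begins with associations between five tissue markers and clinical outcome, but specifies a single comparison. Quartiles are inspected, the marker is dichotomised, and there follows "comparison by response using a Chi-square test or Fisher's exact test depending on sample size". Six blood markers are handled in the same way, also at individual time points on treatment. An optional repeated-measures analysis follows marker levels over time and is not tied to outcome. PFS and survival get Kaplan-Meier curves and disease control gets descriptive summaries, none of them by marker. The section describes the biomarker work as mainly descriptive, sets no alpha for it, and says it will inform selection criteria and validation in future studies.

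Sections 12.1 and 13.1 define response at 6 weeks. The Stage 1 rule in Section 13.1 is: "If 2 or more patients have an objective response after completion of stage 1, an additional 19 patients will be enrolled in stage 2". Section 3 ties the count to the same scan: "If at least 2 objective responses are observed at the first disease re-evaluation at 6 weeks after beginning oral exemestane, Stage 2 will be activated".

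**The concern.** The method covers less than the objective. A yes/no response is the only link between marker and outcome, and the Stage 1 rule itself ensures that a futility stop leaves almost no responders. In that case the by-response table has one column empty or holding a single patient, and the stated question goes unanswered.

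The limit lies in the outcome, so leaving the marker uncut does not remove it. Response also pools stable disease with progression, although the Synopsis lets patients with CR, PR or SD continue treatment. Finer outcome data will exist: Appendix II requires the sum of target-lesion diameters, Section 9.1 schedules CT every 6 weeks, and PFS is a secondary endpoint. At stake is what the correlative objective can deliver. No primary or secondary conclusion depends on it.

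**Working it through.** **Inputs.** Stage 1 n=10, Stage 2 adds 19, continue at 2 or more responders, success at 4 or more of 29 (Sections 3 and 13.1). Response rates 5% (null) and 20% (alternative), type I error 5%, power 80% (Section 13.2). No biomarker alpha is given; two-sided 0.05 is assumed here.

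**1. The plan's own design figure.** P(success) = Σ P(X₁=x)·P(X₂ ≥ 4−x), summed over the x that allow continuation, with X₁ ~ Bin(10,p) and X₂ ~ Bin(19,p).
- Continue at 2 or more (as written): type I error 2.6%, power 59.6%.
- Continue at 1 or more: type I error 4.7%, power 80.1%.

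The stated 5% and 80% are not reproduced by the written rule. That is a separate matter, but it affects how often a Stage 1 stop occurs.

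**2. Probability of a Stage 1 futility stop.** P(X₁ ≤ 1) = (1−p)¹⁰ + 10p(1−p)⁹; P(X₁ = 0) = (1−p)¹⁰.

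| Response rate | Stop at 0 or 1 (as written) | Stop at 0 only |
|---|---|---|
| 5% | 0.599 + 0.315 = 91.4% | 59.9% |
| 10% | 0.349 + 0.387 = 73.6% | 34.9% |
| 20% | 0.107 + 0.268 = 37.6% | 10.7% |

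**3. What the planned test can show after a stop.**
- 0 responders: no comparison.
- 1 responder, marker split m versus 10−m: the responder falls in the smaller group with probability min(m, 10−m)/10, which is the smallest two-sided Fisher p for an unequal split. This gives 0.10 (1/9), 0.20 (2/8), 0.30 (3/7) and 0.40 (4/6). At 5/5 both possible tables are equally likely and p = 1.0.
- Marker left uncut: the exact rank test of 1 versus 9 has minimum p = 2/10 = 0.20.
- Uncorrected chi-square falls below 0.05 only at 1/9 (0.0016) or 2/8 (0.035), where the smallest expected count is 0.1 or 0.2 and the approximation is not valid. With Yates' correction the minimum is 0.16.

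**4. If the trial reaches 29.** The smallest Fisher p at a 14/15 split is 0.22, 0.10 and 0.042 for 2, 3 and 4 responders. At a 7/22 split it is 0.052, 0.0096 and 0.0015. The comparison becomes possible but stays thin.

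**5. Illustrative power of an alternative outcome.** Assumptions, none from the documents: marker and tumour change are bivariate normal with correlation 0.3 to 0.6; response is the tail of tumour change; two-sided 0.05 per marker, unadjusted for 11 markers; no new lesions, non-target progression or ties. Simulated, with several thousand runs per setting.

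| Setting | Fisher, median cut | Rank correlation with percent tumour change |
|---|---|---|
| n=29, 20% response | about 11% to 39% | about 32% to 92% |
| n=10, given a stop (0 or 1 responders), 5% response | 0% | about 12% to 40% |
| n=10, given a stop (0 or 1 responders), 20% response | 0% | about 11% to 33% |

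The ordering is the same at every correlation tried. The absolute gain is modest after a Stage 1 stop and larger at 29.

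**The case against.** The strongest reply is that significance is the wrong yardstick. The plan calls this work exploratory and mainly descriptive and sets no alpha, and using the primary endpoint as the biomarker outcome is conventional. That stands. A reader might infer that a formal test fails, or that the biomarker study could report nothing after a Stage 1 stop. The documents support neither: marker distributions, values on treatment and the immune-response objective in Section 1.3 remain reportable with no responders. What goes unanswered is the link to outcome.

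Second, in an inactive-drug scenario there is little drug benefit for a marker to identify. In a single arm, associations with tumour change or PFS may reflect prognosis or the continuing checkpoint therapy. That also stands, and it limits how the added results may be used.

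Third, the remedy does not rescue a Stage 1 stop. Power there stays at 40% or less even at a correlation of 0.6, before any allowance for 11 markers. The case for adding it is that it costs little and uses information that the planned test discards.

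Fourth, later responses could add to the count. Sections 12.1 and 13.1 fix response at 6 weeks, so this does not change the planned comparison. A toxicity stop under Section 13.4 is a separate route and is not limited to 1 responder.

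**Conclusion.** The point holds as a gap between the correlative aims and the one biomarker-outcome comparison in Section 13.3. After a Stage 1 futility stop that comparison is empty (0 responders) or uninformative (1 responder; smallest two-sided Fisher p 0.10, or 1.0 at a median cut).

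A reader might take 91% as a firm probability of this under a 5% response rate. The documents do not settle it, because that figure rests on the continue-at-2 rule, which gives about 60% power rather than the stated 80%. Under continue-at-1 the stop probability would be 60% at a 5% response rate and 11% at 20%, and a stop would leave no responders at all. The consequence holds under either rule; only its frequency changes. The passages on the Stage 1 rule and on power must be reconciled separately.

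The harm is lost information on an exploratory objective, with no effect on primary or secondary conclusions. The power contrast rests on an assumed correlation of 0.3 to 0.6 and a simplified model, and is illustrative only. The change is worth considering.

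**What to change.** In Section 13.3, keep the by-response tables and add, for each baseline marker left uncut:
- its rank correlation with percent change in the sum of target-lesion diameters at the 6-week scan, with patients who progress early, by new lesions or by non-target disease ranked worst (ties allowed);
- an analysis of PFS by marker;
- CR/PR/SD versus PD, defined explicitly, because Section 13.1 describes disease control through response duration.

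Report estimates with confidence intervals, and state that these analyses are also run if the trial stops at Stage 1. Name Fisher's exact test for the by-response tables when counts are this small.

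**Cost.** Plan wording and a few analyses. No new scans or samples are needed, but percent change is not a named endpoint and must be derived from the recorded sums. The downside is more comparisons across 11 markers, and associations that may be prognostic or due to continuing checkpoint therapy. Label them hypothesis-generating and do not use them alone to set selection criteria for a later study.

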13.4 Monitoring Guidelines

Monitoring guidelines are developed to monitor excess toxicity using a continuous monitoring strategy based on an adaptation of Pocock stopping boundaries.³¹ In the event that a stopping rule is triggered, enrollment will be halted in the affected Treatment Plan. The Treatment Plan will be reviewed by the study committee (PI, co-I's and Statistician) and a decision made about the future of the study. The IRB would be notified in the appropriate manner (expedited or at time of annual continuing review).

13.4.1 Grade 4/5 treatment Related Toxicity

The goal is to construct a boundary based on toxicity such that the probability of early stopping is at most 10% if the toxicity rate is equal to 5% with a sample size of 29. Given these parameters, the upper stopping boundary for toxicity is 2 events out of 7 patients, 3 out of 16, 4 out of 28, or 5 at any time. If the true toxicity rate is as high as 20% then chance of early stopping is 87% and the expected sample size is 13.5.

13.4.2 Grade 3/4/5 Pneumonitis, Colitis, Nephritis, Myocarditis or Hepatitis

The goal is to construct a boundary based on toxicity such that the probability of early stopping is at most 10% if the toxicity rate is equal to 4% with a sample size of 29. Given these parameters, the upper stopping boundary for toxicity is 2 events out of 8 patients, 3 out of 19 or 4 at any time. If the true toxicity rate is as high as 20% then chance of early stopping is 90% and the expected sample size is 11.5.

Due to the addition of stopping rules, it is understood that the overall power may be slightly reduced for this study.

14 Conduct of the Study

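### Section 13.4.2: the printed immune-related toxicity boundary gives 89% stopping and an expected sample size of 12.7 at a 20% rate, not the stated 90% and 11.5

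*Combined protocol and SAP*

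**What the plan says.** Section 13.4 describes toxicity monitoring as a "continuous monitoring strategy based on an adaptation of Pocock stopping boundaries". Section 13.4.2 applies it to the immune-related events. The design goal is that the "probability of early stopping is at most 10% if the toxicity rate is equal to 4% with a sample size of 29". The boundary is "2 events out of 8 patients, 3 out of 19 or 4 at any time". For a true rate of 20%, the section states that the "chance of early stopping is 90% and the expected sample size is 11.5".

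Section 13.4.1 has the same structure for Grade 4/5 treatment-related toxicity, with a 5% reference rate and a boundary of "2 events out of 7 patients, 3 out of 16, 4 out of 28, or 5 at any time". There, at a 20% rate, the "chance of early stopping is 87% and the expected sample size is 13.5".

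No other part of the document gives a different boundary or different figures for the immune-related rule.

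**The concern.** The stopping probability and expected sample size of a continuous boundary are fixed by the boundary, the maximum sample size and the assumed event rate. All three are printed in 13.4.2, so the stated figures should follow exactly. The expected size does not.

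This is one of the trial's two toxicity stopping rules, and it covers the events of most interest when exemestane is added to checkpoint blockade. If the figures came from a boundary with a step that the text lost, the rule that sites apply is not the rule that was evaluated. If the printed boundary is complete, the protocol says the rule reacts somewhat faster than it does. The two possibilities differ in practice for a qualifying event in the first patient: the printed text does not halt enrollment, while a boundary with a first-patient step would.

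**Working it through.** **Inputs, all from section 13.4.** Monitoring after every patient; maximum N = 29; rates p = 4% and p = 20%. The printed boundary halts when cumulative events reach k(n), where k(n) = 2 for patients 1 to 8, 3 for patients 9 to 19, and 4 for patients 20 to 29.

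**Formulas.** Let a(n, e) be the probability of having e events after n patients without having halted, with a(0, 0) = 1. Before the boundary is applied at patient n,

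u(n, e) = (1 − p) · a(n−1, e) + p · a(n−1, e−1).

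The probability of halting at patient n is s(n), the sum of u(n, e) over e ≥ k(n). For e < k(n), a(n, e) = u(n, e). Then

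- P(stop) = Σ s(n), n = 1 to 29
- E[N] = Σ n · s(n) + 29 · (1 − P(stop))

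**Step 1: check the method on 13.4.1.** With 2/7, 3/16, 4/28 and 5 at any time, at p = 20%, P(stop) = 86.69% and E[N] = 13.545. The protocol states 87% and 13.5. At p = 5%, P(stop) = 9.11%, within the 10% goal. The method agrees with the protocol's figures to printed precision.

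**Step 2: the printed 13.4.2 boundary at p = 20%.**

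- By patient 8, the halting probability is 1 − 0.8⁸ − 8 · 0.2 · 0.8⁷ = 1 − 0.1678 − 0.3355 = 0.4967.
- The recursion then gives 0.7883 by patient 19 and 0.8925 by patient 29.
- Mean enrollment among trials that halt is 10.76, so E[N] = 0.8925 · 10.76 + 0.1075 · 29 = 9.60 + 3.12 = 12.72.

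Simulation with 400,000 runs gives 89.3% and 12.70. At p = 4%, P(stop) = 6.99%.

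**Step 3: other readings of the printed rule at p = 20%.**

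| Reading | P(stop) | Size |
|---|---|---|
| As printed, continuous | 89.25% | 12.72 |
| Halt at patient 29 not counted as early | 88.0% | 12.72 |
| Looks only at 8, 19 and 29 patients | 89.25% | 15.65 |
| First two limits one patient lower (2/7, 3/18) | 88.7% | 13.2 |
| Mean size among halted trials only | 89.25% | 10.76 |
| **Stated in 13.4.2** | **90%** | **11.5** |

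None gives 11.5.

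**Step 4: a boundary that does give the stated pair.** Keep the printed limits and add a halt if the first patient has an event (1 of 1):

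| | Printed | Printed plus 1 of 1 | Stated |
|---|---|---|---|
| P(stop) at 4% | 6.99% | 9.72% | at most 10% |
| P(stop) at 20% | 89.25% | 89.87% | 90% |
| E[N] at 20% | 12.72 | 11.49 | 11.5 |

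The extra step fits a Pocock-type construction, which uses a constant pointwise level. At p = 4%, the probability of at least 1 event in 1 patient is 0.0400, of at least 2 in 8 is 0.0381, and of at least 3 in 19 is 0.0384. A pointwise level of 0.04 therefore admits all three. The next wider boundary in that family halts with probability 10.02% at a 4% rate, over the limit. Adding 1 of 1 to the 13.4.1 boundary would give 12.3% at its 5% rate, also over the limit. That would explain why only 13.4.2 shows a mismatch.

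**The case against.** The arithmetic is not seriously disputable; the argument is about weight.

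- **The 90% figure is close.** It differs from 89.25% by 0.75 points and would not merit comment alone. That stands: the point rests on the expected size.
- **The printed rule meets its only stated constraint.** It halts with probability 7.0% at a 4% rate, against a limit of 10%; the 90% and 11.5 are descriptive. That also stands, and it is why this is not a critical defect.
- **The missing first-patient step is an inference.** Boundaries with altered limits, such as 2/11, 3/22, 4/28, also give about 90% and 11.5. True, but they are not the printed rule. Of the boundaries tried, adding 1 of 1 was the only match that keeps the printed limits. The mismatch does not depend on the explanation.
- **Practical effect is limited.** At a 20% rate the cumulative halting probability by patient 10 is 51% as printed and 55% with the extra step; by patient 20 it is 79% and 80%. A trigger leads to committee review, and each qualifying event is reported individually under section 10.3. Both expected sizes also ignore the Simon futility stop after 10 patients. All of this is fair. Reporting an event does not itself halt enrollment, though, so the first-patient question remains.
- **The printed rule can be applied as written.** It can, but then the figures printed beside it describe something else.

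**Conclusion.** The concern holds. The expected sample size in 13.4.2 does not belong to the boundary in 13.4.2. At a true 20% rate the printed rule enrolls 12.7 patients on average, not 11.5: 12.72 − 11.5 = 1.22 patients, or 1.22 / 11.5 = about 11% more. Its stopping probability is 89.3%, and its false-alarm probability at 4% is 7.0%.

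This rests on a look after every patient, independent events at a constant rate, a maximum of 29 patients, and no account taken of the efficacy stop at stage 1. The agreement with 13.4.1 supports the same conventions here. That a first-patient halt was used in the calculation and left out of the text is the likely explanation, but the document does not say so. The matter should be corrected; it does not threaten the primary inference or the stated 10% limit.

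**What to change.** Reconcile boundary and figures in 13.4.2, after checking the calculation that produced them.

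- If the printed boundary is the intended one, restate its properties: stopping probability 7% at a 4% rate and 89% at a 20% rate, with an expected sample size of 12.7.
- If the calculation used a further boundary step, write that step into the section, so that the rule applied is the rule evaluated.

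Which rule is appropriate is for the study team to decide. The change is one sentence and does not touch the sample size or the primary analysis. The price is either a slightly less favourable expected size, or one added boundary step with a false-alarm probability of 9.7% instead of 7.0% at a 4% rate if that step is 1 of 1.

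### Two separately calibrated toxicity boundaries halt the same single arm, but the plan gives neither their joint crossing probability (10.3% to 15.6% at its reference rates) nor the power this can cost

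*Combined protocol and SAP*

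**What the plan says.** Section 13.2 bases the sample size on a Simon optimal two-stage design with "type I error of 5% and power of 80" percent, a null response rate of 5% and an alternative of 20%. The synopsis and sections 3 and 13.1 print the decision rule as 2 or more responses in the first 10 patients, then 4 or more in 29.

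Section 13.4.1 sets a boundary for Grade 4/5 treatment-related toxicity so that "the probability of early stopping is at most 10% if the toxicity rate is equal to 5% with a sample size of 29". The boundary is "2 events out of 7 patients, 3 out of 16, 4 out of 28, or 5 at any time". At a 20% toxicity rate the section reports that the "chance of early stopping is 87% and the expected sample size is 13.5".

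Section 13.4.2 sets a second boundary, for Grade 3 to 5 pneumonitis, colitis, nephritis, myocarditis or hepatitis, so that "the probability of early stopping is at most 10% if the toxicity rate is equal to 4% with a sample size of 29". The boundary is "2 events out of 8 patients, 3 out of 19 or 4 at any time", and at 20% the "chance of early stopping is 90% and the expected sample size is 11.5". The section closes with "Due to the addition of stopping rules, it is understood that the overall power may be slightly reduced for this study".

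Under section 13.4 a triggered rule halts enrollment. The study committee, which includes the statistician, then decides what happens to the study.

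**The concern.** The trial has one arm, so crossing either boundary halts the whole trial. The chance that at least one is crossed is larger than either chance alone, and the plan does not report it. The 80% in 13.2 is power before any safety stopping, and the only qualification is an adverb with no number behind it.

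Two readings are affected. A study committee looking at a halt should know how often one would occur at the very rates the plan uses for calibration. A reader of a negative result should know how much of the stated power could be lost to halts that have nothing to do with response.

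**Working it through.** **Inputs.** Boundaries and reference rates are from 13.4.1 and 13.4.2; response rates of 5% and 20% from 13.2; the two-stage rule from 13.1. The documents do not say how often one event counts toward both boundaries, so overlap is an assumption, varied from disjoint to fully nested. Toxicity is assumed independent of response.

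**Method.** The event count is followed patient by patient. A boundary such as 2 out of 7 is read as 2 or more events at any point up to patient 7, and so on to patient 29. All probabilities are exact.

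**Reproducing the plan's own figures.**
- 13.4.1 alone: 9.1% stopping at a 5% rate. At 20%, 86.7% stopping and expected sample size 13.5. All agree with the plan.
- 13.4.2 alone: 7.0% stopping at a 4% rate. At 20%, 89.3% stopping against the stated 90%, and expected sample size 12.7 against the stated 11.5. The stopping probability agrees closely; the expected sample size is 1.2 patients higher than printed.
- Two-stage design: power = Σ over x ≥ r of P(X₁ = x) × P(X₂ ≥ 4 − x), with X₁ binomial on 10 patients and X₂ on 19. With r = 1, type I error is 4.7% and power 80.1%, matching 13.2. With the printed r = 2, they are 2.6% and 59.6%.

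**Joint crossing.** Both counts are followed together. With rates of 5% and 4%, each patient has both events with probability c, only the first with 0.05 − c, only the second with 0.04 − c.

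If every halt is final and scored as no success, power = two-stage power × (1 − joint crossing probability). For disjoint events with r = 1: 0.801 × (1 − 0.156) = 0.676.

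| Overlap | c | At least one boundary crossed, 29 patients | Power, 1 or more of 10 (base 80.1%) | Power, printed 2 or more of 10 (base 59.6%) |
|---|---|---|---|---|
| Disjoint | 0 | 15.6% | 67.6% (−12.5 points) | 50.3% (−9.3) |
| Independent | 0.002 | 15.5% | 67.7% (−12.4) | 50.4% (−9.2) |
| Half nested | 0.02 | 13.8% | 69.1% (−11.0) | 51.4% (−8.2) |
| Fully nested | 0.04 | 10.3% | 71.9% (−8.3) | 53.5% (−6.1) |

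Full nesting is an extreme. It requires every counted immune event to be a treatment-related Grade 4 or 5 event, whereas 13.4.2 also counts Grade 3 events, which cannot count toward 13.4.1.

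**Allowing for trials that end at the Stage 1 look.** Some trials stop for futility at 10 patients before a boundary is reached. At a 20% response rate a toxicity halt then occurs in 9.8% to 14.8% of trials with 1 or more of 10, and in 8.5% to 12.9% with 2 or more of 10.

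**A more lenient scoring.** If a trial halted with 4 or more responses already seen counts as a success, the loss is 5.6 to 8.7 points with 1 or more of 10, and 3.9 to 6.0 points with 2 or more of 10.

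**Lower toxicity (illustration; the rate is an assumption).** With 2% for each event type and every halt final, power with 1 or more of 10 is 78.0% to 78.9%, a loss of 1.2 to 2.1 points.

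**The case against.** The plan contradicts none of its own safety figures here. Each section promises at most 10% at its own rate and delivers it. Neither promises 10% jointly, so a reader who infers that a limit has been breached goes beyond the text. The plan also admits a power loss. All of this stands, and it makes the fault one of reporting.

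A reader might also take 12 points as the loss in this trial. The documents do not support that, for three reasons. That figure belongs to a Stage 1 threshold they do not print; under the printed rule the largest loss is 9.3 points. It needs every halt to be final, while section 13.4 provides for review and a decision. It also needs true toxicity at 5% and 4%, which are calibration rates. Section 6.1.1 expects no change in toxicity from the combination, and exclusion 4.2.2 removes patients with ongoing immune toxicity of Grade 2 or above. At lower rates, or with halts that are reviewed and lifted, a slight reduction could be an accurate description.

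What does not stand is the conclusion that nothing needs saying. The stopping probabilities and expected sample sizes in 13.4 themselves treat a crossing as the end of enrollment, at specified rates. On that same convention, at the plan's own reference rates, the loss is 6 to 12 points across the two thresholds.

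**Conclusion.** The point holds as an unquantified and, on the plan's own convention, understated operating characteristic. At 5% and 4%, at least one boundary is crossed in 10.3% to 15.6% of trials that would enroll all 29 patients. With every halt final, power at a 20% response rate falls by about 8 to 12 points with 1 or more of 10, or about 6 to 9 points with the printed 2 or more. For the design that matches 13.2, the chance of missing an active treatment becomes 28% to 32% against the stated 20%.

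These figures assume independence of toxicity and response, and they are an upper range for the reasons given above. They do not show that either boundary is miscalibrated or that it should be loosened. The gap between the printed Stage 1 rule (59.6%) and the stated 80% is about 20 points. It is larger than the effect described here and determines which set of figures applies. The unreproduced 11.5 in 13.4.2 does not alter the conclusion, since the stopping probability of that boundary agrees with the plan.

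**What to change.** First reconcile the Stage 1 threshold in the synopsis and sections 3 and 13.1 with the power stated in 13.2.

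Then replace the closing sentence of 13.4.2 with text to this effect: at true rates of 5% and 4%, at least one boundary would be crossed in 10.3% to 15.6% of trials that would enroll all 29 patients, depending on event overlap; in the worst case, where every halt ends the study without success, power at a 20% response rate would be 67.6% to 71.9% (if the reconciled threshold is 1 or more of 10) or 50.3% to 53.5% (if it is 2 or more of 10). Print only the set that applies. If the chance of an actual halt is quoted, use the figures that allow for the Stage 1 look. Show the same worst-case power beside the unadjusted figure in 13.2, and recheck the expected sample size in 13.4.2.

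The cost is a few sentences and a less favorable stated power. Boundaries, sample size and patient management do not change.
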